Normally distributed continuous data were presented as mean and standard deviation (SD) while non-normally distributed continuous data by the median and interquartile range (IQR), and the dichotomous data were computed using frequency and percentage. The rates and their 95% confidence intervals (CIs) were calculated for the primary endpoint and the secondary endpoints. The hazard ratio (HR) was estimated with or without adjustment for covariates using Cox regression models. Significant variables in the univariate analysis and other variables of interest were included in the subgroups to investigate the potential influences on the resolution of the thrombus, where continuous variables were dichotomized based on the median value. A forest plot was created to display subgroup analysis. To test for changes in diffusion data across different time points of thrombus resolved vs. thrombus unresolved (including reduced, unchanged, and enlarged thrombus), linear mixed models were tested using the *lme* function in R. To investigate any significant interactions in more detail, we then ran corresponding pairwise comparisons using the *emmeans* function in R. Comparisons were regarded as two-sided, and statistical significance was determined by the P value of 0.05. All analyses were scheduled for completion with R version 3.5.1 (The R Project for Statistical Computing, Vienna, Austria).

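### Variables that enter the subgroup display because they were significant on univariate analysis will, on average, show exaggerated hazard ratios, with P values and intervals that ignore the selection

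*Combined protocol and SAP*

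**What the plan says.** All of the relevant text is in the Statistics Analysis Plan.

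- Effect measure: "The hazard ratio (HR) was estimated with or without adjustment for covariates using Cox regression models". The covariates are not named.
- Entry to the subgroup analysis: "Significant variables in the univariate analysis and other variables of interest were included in the subgroups". This gives two routes, significance on a univariate screen and interest. Neither the screened variables nor the variables of interest are listed or counted.
- Coding: "continuous variables were dichotomized based on the median value".
- Display: "A forest plot was created to display subgroup analysis". The plotted statistic is not named.
- Threshold: "Comparisons were regarded as two-sided, and statistical significance was determined by the P value of 0.05". Subgroups are not exempted.

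Only one efficacy set is defined, made up of patients who completed treatment and follow-up. The plan describes no hold-out sample, resampling, shrinkage, multiplicity control or selection-adjusted interval.

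**The concern.** The same data appear to choose the variables and then supply the estimates shown for them. A variable that gets in because P was below 0.05 has an estimate from the tails of its sampling distribution. Its average distance from 1 is therefore too large, and an ordinary 95% interval or P value, calculated as if the variable had been fixed beforehand, does not have its stated meaning. This happens even when the plan is followed exactly.

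At stake is the plan's only analysis of what influences thrombus resolution; the mixed models compare groups already defined by whether the thrombus resolved. Weak or null predictors that pass the screen would look strong, and readers who form hypotheses from the plot would be misled about their size.

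**Working it through.** **Inputs from the documents.** Two-sided 0.05; Cox hazard ratios; continuous variables split at the median, so roughly 50:50. The plan has no figure to reproduce: it states no sample size, event count, effect size or number of candidates.

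**Assumptions.** About 50 resolution events (for example 75 patients with 66% resolved: 75 × 0.66 = 49.5); the univariate screen uses the Cox model; the same median split is used in the screen and in the display.

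**Formulas.** For a 50:50 split with D events, the estimated log HR is approximately normal with SE s = 2/√D. Let m = log(HR)/s, U = P(Z > 1.96) and L = P(Z < −1.96), where Z ~ N(m, 1), and let φ be the standard normal density.

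- Chance of entry: p = U + L.
- Mean |Z| given entry: [m(U − L) + φ(1.96 − m) + φ(1.96 + m)]/p. Displayed HR = exp(s × that mean), with wrong-direction estimates inverted.
- Coverage given entry, for the HRs worked below: (U − 0.025)/p.

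**D = 50.** s = 2/√50 = 0.2828. The smallest HR that can pass is exp(1.96 × 0.2828) = 1.74.

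- True HR 1.3: m = 0.928, U = 0.1509, L = 0.0019, p = 0.153. Mean |Z| = (0.1382 + 0.2403)/0.1529 = 2.476. Displayed HR = exp(0.700) = 2.01. Coverage = 0.1259/0.1529 = 82%.
- True HR 1.5: m = 1.434, p = 0.300. Mean |Z| = (0.4285 + 0.3486)/0.2996 = 2.594. Displayed HR = exp(0.734) = 2.08. Coverage = 0.2743/0.2996 = 92%.
- True HR 3.0: m = 3.884, p = 0.973. Mean |Z| = 3.949. Displayed HR = exp(1.117) = 3.05. Coverage = 0.9478/0.9728 = 97%.

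Without selection, coverage is 95% throughout.

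**Other event counts.** Displayed HR, with coverage given entry:

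| Events | Smallest HR that passes | True 1.5 | True 2.0 | True 3.0 |
|---|---|---|---|---|
| 20 | 2.40 | 3.02 (82%) | 3.23 (93%) | 3.77 (96%) |
| 40 | 1.86 | 2.24 (90%) | 2.46 (96%) | 3.13 (97%) |
| 80 | 1.55 | 1.83 (94%) | 2.11 (97%) | 3.00 (95%) |
| 150 | 1.38 | 1.63 (96%) | 2.01 (96%) | 3.00 (95%) |

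**Cox simulation with scans at 6 and 12 weeks** (75 patients, about 66% resolved, Efron ties, 1,500 trials per setting): true 1.3 is displayed as 2.04 (85% coverage), 1.5 as 2.12 (92%), 2.0 as 2.35 (97%) and 3.0 as 3.04 (98%). These agree with the approximation.

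**Different coding at the two steps.** If the continuous form is screened and its median split is then displayed (100 patients, about 62 events), the mean HR is 1.28 over all trials and 1.64 among those selected. For a stronger effect the figures are 1.63 and 1.77, and for a null variable 1.00 and 1.56, with 33% of selected nulls reaching P < 0.05. The bias is weaker but remains. That run used Breslow ties, which made its unselected intervals conservative (coverage about 99%).

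**The case against.** The strongest reply is that this is an exploratory study by title, that the sentence sets out only to look at potential influences, and that the primary and secondary rates with their intervals do not depend on it. That stands, and it limits the priority. It does not remove the bias: the 0.05 rule is applied without exempting subgroups, and inflated estimates do their harm when hypotheses are being formed.

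Several stronger readings are tempting, and the documents do not support them.

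- *The whole forest plot is exaggerated.* The same sentence has a second route, for variables of interest. If these are chosen without regard to outcome, this mechanism does not touch them. Because they are not listed, however, the plan does not guarantee that they will be.
- *The intervals are invalid.* At high power they behave almost nominally. In the table, once power reaches about 87% (for example 80 events and a true HR of 2.0), the displayed log HR is at most about 8% too large.
- *Coverage is 0% for a null variable.* With the same coding at both steps this is true by construction, since passing the screen means that the interval excludes 1. It says nothing specific about this study, and it fails when the coding changes between steps.
- *Ten or twenty null candidates give a 40% or 64% chance of a false predictor.* The arithmetic is right for independent tests (1 − 0.95^10 = 0.401; 1 − 0.95^20 = 0.642), but this is ordinary multiplicity. A fixed list of the same length tested at 0.05 would carry the same risk, and the number of candidates is not given.

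Two gaps in the text also limit certainty. That the plot shows Cox hazard ratios is the likely reading, since no other effect measure for predictors appears, but it is not stated. Nor does the plan say whether continuous variables are screened before or after splitting, or whether non-significant results are withheld.

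**Conclusion.** The concern holds for variables admitted through the univariate screen. Their displayed hazard ratios will be too far from 1 on average, and their nominal P values and intervals ignore how they were chosen. The distortion is large for weak effects or few events and close to nil for strong effects with ample events. Its size in this study cannot be fixed from the documents: the figures rest on an assumed event count, an even split and the same coding at both steps. This is a cheap improvement of low to moderate priority, confined to the exploratory analysis of predictors.

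**What to change.** Amend the Statistics Analysis Plan as follows.

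1. Remove univariate significance as a criterion for entry to the subgroup analysis.
2. Fix a short list of baseline variables before looking at outcomes. Candidates, as far as they are recorded, are age, renal function, underlying disease, baseline thrombus size, prior anticoagulation and single antiplatelet use. Some of these appear in the protocol only as eligibility text, so confirm that they are captured. Renal function is also tied to dose reduction under Study treatments, so its estimate needs cautious reading.
3. Display every listed variable whatever its P value, and state what the forest plot shows.
4. Report estimates and intervals as hypothesis-generating, without labelling any as significant.
5. If screening is kept, report all screened variables and their number, state the coding used at each step, and add bootstrap- or shrinkage-corrected estimates.
6. Optionally, show continuous variables per SD alongside the median split.

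The cost is a change of wording and slightly more analysis, with no new data if the listed items are recorded. The downside is fewer nominally significant predictors. A fixed list does not by itself control multiplicity, so keep it short and keep the hypothesis-generating label.

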Note: In patients with LV thrombus complicated with hemorrhagic stroke \geq 4 weeks or recent ischemic stroke/transient ischemic attack, the investigators decided whether anticoagulation therapy can be given according to the specific situation.

Study treatments

The enrolled patients were assigned to a standard dose of rivaroxaban 20 mg qd (it can be reduced to 10-15 mg qd depending on the patient's condition and renal function) after the confirmation of LV thrombus by contrast-enhanced echocardiography.

Study endpoints

The primary endpoint of this study was the LV thrombus resolution rate at 12 weeks confirmed on contrast-enhanced echocardiography.

The secondary endpoint events:

- 1) the LV thrombus resolution rate at 6 weeks, the LV thrombus resolution or reducing rate at 6 weeks, the LV thrombus unchanging or increasing rate at 6 weeks, the LV thrombus resolution or reducing rate at 12 weeks, and the LV thrombus unchanging or increasing rate at 12 weeks. (disappearance of thrombus as an indicator of resolution rate, $>15\%$ reduction in thrombus length or thickness measured by ultrasonography as an indicator of reduction rate, $\leq 15\%$ variation in length or thickness as an indicator of unchanged rate, and $>15\%$ increase in length or thickness as an indicator of increasing rate)
- 2) incidence of the composite of stroke, systemic embolism, myocardial infarction, and cardiovascular death during follow-up
- 3) major bleeding according to the International Society on Thrombosis and Haemostasis [ISTH] criteria and clinically related non-major hemorrhage events during follow-up.

An adverse event was any adverse medical event, including an exacerbation of a pre-existing condition or abnormal laboratory findings on clinical examination of a subject on medication, which was not necessarily related to such treatment. A serious adverse event can be fatal, life-threatening, requiring hospitalization or prolongation of an ongoing hospital stay, resulting in persistent or significant disability/incapacity, and it was any adverse medical event that represents a significant risk of congenital

anomalies/birth defects and/or other clinically significant serious events.

Study procedures

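### The SAP's linear mixed model is written for a response the trial does not list and for groups with no stated classification visit, so it cannot be run as written

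*Combined protocol and SAP*

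**What the plan says.** The Statistics Analysis Plan gives one sentence to the mixed model. Its purpose is "To test for changes in diffusion data across different time points of thrombus resolved vs. thrombus unresolved", and it is fitted with the R function *lme*. The comparison group pools three categories: "thrombus unresolved (including reduced, unchanged, and enlarged thrombus". The next sentence covers follow-up with *emmeans*: "To investigate any significant interactions in more detail, we then ran corresponding pairwise comparisons". Tests are two-sided at 0.05.

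Under Study endpoints, resolution is defined by "disappearance of thrombus as an indicator of resolution rate". It is an endpoint at two visits. The primary endpoint is "the LV thrombus resolution rate at 12 weeks confirmed on contrast-enhanced echocardiography", and one of the secondary endpoints is "the LV thrombus resolution rate at 6 weeks".

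Study procedures schedules blood tests and contrast echocardiography at baseline, 6 weeks and 12 weeks, and thrombus size is recorded.

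**The concern.** A mixed model needs a response, a grouping rule, a time factor and a random structure. Here the named response is not something the protocol says it measures, and the grouping rule has no visit attached. Two analysts working from this text could fit different responses to different groups and both claim to have followed the plan.

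The missing response matters because the two plausible candidates lead to different problems. If it is thrombus size, part of the comparison restates how the groups were made. If it is a laboratory marker, nothing is circular. But the list of blood tests in Study procedures is open-ended, so markers could be picked after the data are seen and then tested at 0.05 between groups formed by an outcome.

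**Working it through.** The documents give no sample size, thrombus dimensions or resolution rate for this analysis, so there is no stated figure to reproduce. The check is a comparison of the text, plus short algebra for the size reading.

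**1. Response against what is collected.**
- Study endpoints: rates of resolution, reduction, no change and increase (from measured length or thickness), a clinical composite, and bleeding.
- Study procedures: haematology, liver and kidney chemistry, clotting tests, and thrombus size on contrast echocardiography.
- Statistics Analysis Plan: diffusion data.

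The SAP's term matches none of the items in the first two lists, and it appears nowhere else in the document.

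**2. Visit that forms the groups.** The SAP says which categories count as unresolved, but not when status is taken. Three readings are open. Take a patient with thrombus at week 6 and none at week 12:
- by week-6 status, unresolved;
- by week-12 status, resolved;
- by status updated at each visit, unresolved at week 6 and resolved at week 12.

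**3. Size reading, contrast at the defining visit.** Let bR and bU be the mean baseline sizes of the resolved and unresolved groups, and u the unresolved group's mean size at the defining visit. Resolution means disappearance, so the resolved mean at that visit is 0. Unresolved patients still have thrombus, so u > 0.

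Contrast (resolved minus unresolved) = 0 − u = −u.

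This is nonzero whatever the treatment does. A P value for it tests the definition of the groups.

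**4. Size reading, interaction between baseline and the defining visit.**
- Change in resolved patients = 0 − bR.
- Change in unresolved patients = u − bU.
- Interaction = (0 − bR) − (u − bU) = (bU − u) − bR.

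With equal baselines (bR = bU) this reduces to −u, again nonzero, so a significant interaction is likely. It is not automatic, because the interaction is zero whenever bR = bU − u. As an illustration with assumed values, take bU = 20 mm, 50% shrinkage in unresolved patients (u = 10 mm) and bR = 10 mm: (20 − 10) − 10 = 0. The interaction therefore mixes the grouping rule with both baseline means and the remaining size.

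**5. Size reading, other visits with week-12 groups.** Baseline size is measured before resolution and is not fixed by the grouping. Week-6 size is partly tied to it, because patients already clear at week 6 contribute zeros.

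**6. Marker reading.** A blood marker does not enter the definition of resolution, so neither its group contrast nor its interaction is fixed by definition. Resolution is itself a post-baseline outcome, however, so a difference describes patients who did and did not clear. It does not show an effect of treatment or of the marker.

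**7. Reach.** For the endpoints the SAP states: "The rates and their 95% confidence intervals (CIs) were calculated for the primary endpoint and the secondary endpoints". None of those estimates uses the mixed model.

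**The case against.** Several points on the other side stand.

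- **The model is not wholly unspecified.** The text gives the make-up of the groups, a time factor, the fitting function and follow-up of interactions. Group, time and their interaction can be inferred as fixed effects. A reader might infer that everything about the model is open, but what is actually open is the response, the classification visit and the random structure. The last is missing detail rather than an error.
- **The pairwise contrasts are conditional.** The plan runs them only to explore a significant interaction. A reader might infer that a definitional week-12 contrast is bound to be reported as a finding. The documents do not support that, since step 4 shows that the interaction can be zero.
- **Week 12 is the natural guess for the groups,** being the primary endpoint visit. That is reasonable, but the SAP does not say it, and settling it would leave the response undefined.
- **This may be a slip of wording in a study titled exploratory.** That is possible. The documents still do not show which measurement was intended, and the answer decides whether some of the tests mean anything. A reader might equally infer that an undeclared imaging measure was collected; nothing in the endpoints or procedures supports that either.

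**Conclusion.** The point holds in limited form. As written, the mixed model cannot be run: its response matches no endpoint or measurement in the protocol, and the visit separating resolved from unresolved is not given.

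The conclusion about circularity is conditional. It applies only if thrombus size was meant, and then strictly to the group contrast at the defining visit. It would be wrong to call the whole model circular: baseline size and laboratory markers are not fixed by the grouping.

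No numerical magnitude should be attached. Any rejection rate or reclassification share would rest on assumed sample sizes, dimensions and resolution rates. What can be said without assumptions is that the week-12 size contrast between week-12 groups is nonzero by construction.

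This is an ancillary analysis. It should be corrected, but the primary and secondary results do not depend on it.

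**What to change.** In the Statistics Analysis Plan:

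1. Replace diffusion data with the named measurements recorded at baseline, 6 and 12 weeks.
2. Define resolved and unresolved by week-12 status, the primary endpoint visit.
3. If thrombus size is analysed, do not test it between the groups at week 12. Report any interaction that includes week 12, and any week-6 size comparison, as descriptive only. The SAP's existing summaries serve for this: mean and SD, or for "non-normally distributed continuous data by the median and interquartile range (IQR"). Baseline size may stay as a predictor of resolution.
4. If laboratory markers are analysed, list them in advance and label their comparison by resolution status as descriptive.

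The random effect can be named in the same edit.

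The cost is SAP wording only, with no new data or visits. On the size reading, the P values for week-12 contrasts, for interactions that include week 12 and for week-6 comparisons are given up. On the marker reading, the analysis stays and gains a marker list and a label.
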